9.2 Aim 3 statistical analyses

Costs will be calculated from three distinct perspectives. First, we will take the perspective of AMPATH as a provider of care. Total costs will be defined as the sum of fixed and variable costs. Variable costs for each patient will be calculated by multiplying the number of units of each good or service used by the unit cost. Costs of ART will be obtained from the official AMPATH/PEPFAR supplier in Kenya. Unit costs for non-ARV drugs will be estimated by reviewing invoices and interviewing key informants. Clinical care unit costs will be estimated by multiplying the time of the clinical interaction (based on time motion logs) by the amount spent on staff salaries by level (medical officer, nurse, etc.) and overhead. All costs incurred by the project, not directly attributable to individual participants will be considered as part of the fixed costs. These are usually costs that are exercised regardless of the volume of participants (cleaning, maintenance, utilities, etc.). Fixed costs will also include any equipment bought (new testing machines, motorcycle, rent/space costs, etc.) which will be discounted at a rate of 5% per year to account for depreciation. Total fixed costs will be allocated to all the participants proportionally. Second, we will take into account costs from the patients point of view, which will include time and transport costs to the place where care is received (i.e., the clinic for the SOC vs. the microfinance meeting place for the MF+ICB group). Third, we will perform a potential cost-saving estimation from the point of view of government and donors where financial outlays are compared into the future to gauge the extent to which the proposed intervention can be financially self-sustained.

Effectiveness: We will use the changes in primary and secondary outcomes, as explained in Aim 2; namely: viral suppression and retention-in-care. The incremental effectiveness (ΔE) will be defined as the difference in outcomes between the SOC and the intervention groups.

Incremental Cost-Effectiveness Ratio (ICER) will be defined as incremental cost over incremental effectiveness ($\Delta C/\Delta E$). In addition, we will model incremental costs per disability-adjusted life year (DALY) averted to make the results comparable to the international cost-effectiveness literature. We will model the effects over the life span using the Sullivan method discounting future effects. For the net benefits estimation, we will transform costs into constant 2018 USD using the Kenyan consumer price index and the international average exchange rate to convert from Kenyan shillings (KES) to USD. We will compare the cost per DALY saved to the Kenyan income per capita (GDPpc) and deem the intervention extremely cost-effective if \$/DALY is less than 1*GDPpc, highly cost-effective if \$/DALY is less than 3*GDPpc.

Sensitivity Analysis: We will use sensitivity analyses to describe the scope and nature of the inherent uncertainties surrounding the cost-effectiveness estimates. Each parameter in the model will be varied across a plausible range of in a series of one-way sensitivity analyses and those that exhibit the largest magnitude of influence either in effects, costs, or the resultant cost-effectiveness ratio, will be varied together in multi-way sensitivity analyses. In addition, we will conduct threshold analysis, whereby we will point out the values at which the intervention options may no longer be cost-effective; we will use a probabilistic uncertainty analysis for the variables that have an underlying probability distribution.

The final cost-effectiveness results will be measured with incremental cost effectiveness ratios comparing the SOC with each of the additional interventions. In addition, given that each of the innovations may have an optimal level of scale and diffusion, and potential cost savings from the perspective of each of the actors. To estimate return on investment we will use a cost-utility approach that we have successfully used for HIV testing and can be adopted for HIV treatment retention interventions.

10. Protection of human subjects

This study involves research that is classified as non-exempt human subjects research. All procedures of this research will be conducted in accordance with 45 CFR Part 46 and will be approved by the Moi University School of Medicine IRB (the IRB of record) and the Brown University Institutional Review Board (the prime award recipient).

10.1Risks to human subjects

Participation in this study involves no physical risk above the risks ordinarily encountered in daily life. There may be several non-physical risks associated with study participation.

- 1. There is a small risk of loss of privacy or confidentiality for participants in the trial (Aim 1) and in the qualitative study (Aim 2). Individuals will provide information regarding sensitive topics, such as their experiences with HIV care. All data will be de-identified to ensure no loss of privacy or confidentiality as described in the Data Safety and Monitoring Plan. All informed consent documents will provide participants with information regarding the potential risks of loss of privacy.
- 2. Participants may experience psychological discomfort during the qualitative interviews (Aim 2) or during care sessions (Aim 1), however this should not be beyond what would be experienced during the course of routine care. Interviewers, research assistants and providers will be trained to handle emotional responses to the topics. We will take steps to minimize the psychological discomfort of participating in this study.
- 3. There is a small risk of stigma related to study participation. Individuals will be recruited into the study based on their HIV-status. In order to ensure that participants are not stigmatized based on participation in the study, we are intentionally operating our study within already existing microfinance groups. Microfinance groups are only eligible for study participation if at least 70% of their members are HIV positive. Therefore, there should be no additional stigma associated with our study.
- 4. Potential risks for this study include a minimal physical risk of bruising or discomfort from needle sticks during venipuncture to collect blood. However, every precaution will be taken to reduce the risk of the blood draw by hiring seasoned and proficient phlebotomists. From our prior experience performing blood draws as part of RCTs, the discomfort associated with venipuncture is trivial.

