9.1 Aim 3 procedures

Costs attributable to the intervention will be collected during the randomized controlled trial (Aim 1) for each relevant study period at 6, 12, and 18 months. Costs will be recorded using a cost tracking tool developed specifically for this study. We will estimate differences in the intervention arms (MF+ICB and MF+SOC) and the controls (SOC). The differences in costs among the control and intervention arms will be defined as the incremental costs (Δ C). Cost estimates for the controls will be obtained from

AMPATH's existing electronic medical records (AMRS) as well as accounting and administrative records, and interviews with n=5 key informants such as administrative directors, comptroller, and local managers. In particular, we will use project and administrative records to conduct a cohort-based, microcosting approach. We will assess cost differences between the control and intervention arms including the total costs of the medications (ART, NCD control, etc.), as well as transportation and wait time costs. For each participant, we will review the AMRS to determine the actual utilization of ART, non-ART drugs, laboratory tests used, and clinic visits for each patient.

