- 1. The eligibility criteria in the original project protocol required that a group had to be an active, AMPATH-affiliated Group Integrated Savings for Health Empowerment (GISHE) group in order to enroll in the study. This criterion was revised during the recruitment period such that any active, community-based microfinance group (GISHE and non-GISHE) were eligible to enroll in the trial as long as a majority of their members received HIV-related care at an AMPATH facility. This change was made to maximize sample size given that many GISHE groups had transitioned to community ART groups at the time of study recruitment.
- 2. The original protocol stated that, among microfinance groups randomized to the intervention arm, integrated community-based care visits would occur monthly during months 1-6 of the trial and then quarterly for the remaining months (i.e., months 7-18 of the trial).

Starting in October of 2021, integrated care visits were no longer delivered monthly during months 1-6 of the trial, and instead were delivered less frequently during months 1-6. Specifically, microfinance group enrollment and follow-up occurred in four phases, such that:

- Phase I intervention groups in Busia and Trans Nzoia County received monthly visits during months 1-6 of the trial, and quarterly visits thereafter (in accordance with the original protocol).
- Phase II intervention groups in Trans Nzoia County received monthly visits during months 1-6 of the trial, and quarterly visits thereafter.
- Phase II, Phase III and Phase IV intervention groups in Busia County received monthly visits during the first three study visits (i.e., months 0 2 of the trial), and quarterly visits thereafter (i.e., from months 3 18).

This change to the intervention delivery schedule was made to reduce administrative burden on clinical officers and study staff traveling to remote community meeting locations. Quarterly (rather than monthly) visits were still in keeping with AMPATH care protocols which most commonly recommend quarterly ART distribution for clinically stable HIV patients.

3. The original project protocol stated that integrated community-based care would be delivered to intervention groups at monthly microfinance group meetings by a clinical team comprised of the same cadre of workers who deliver care in AMPATH-supported facilities (clinical officer, pharmacy technician, peer navigator, social worker).

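### The fixed-cost rule in section 9.2 can remove costs incurred only for community care from the incremental cost, so the provider-perspective ICER for MF+ICB can be mis-stated

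*Combined protocol and SAP*

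**What the plan says.** Section 9.2, under the provider perspective: "Total costs will be defined as the sum of fixed and variable costs". The fixed part is a residual category: "All costs incurred by the project, not directly attributable to individual participants will be considered as part of the fixed costs". General running costs belong to it: "These are usually costs that are exercised regardless of the volume of participants (cleaning, maintenance, utilities, etc".) So do purchases: "Fixed costs will also include any equipment bought (new testing machines, motorcycle, rent/space costs, etc".) The pool is then shared out: "Total fixed costs will be allocated to all the participants proportionally". The sentence names neither the arms nor the base (heads, visits or time) for the shares.

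Section 9.1 takes the difference between arms: "The differences in costs among the control and intervention arms will be defined as the incremental costs". Section 9.2 divides this by the difference in effect to obtain the ICER.

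Two other places bear on the rule. Section 9.1 collects costs attributable to the intervention with a study-specific tracking tool and takes control costs from AMPATH records and key informants. Section 10.2 lists the costing steps, among them annualising programme equipment and, separately, adding organisational costs not attributed to a programme. Neither says to which arm a fixed cost is charged.

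**The concern.** A cost that exists only because care is taken to the community should raise the cost of Arm A and of no other arm. If it is pooled and spread over everyone, it is counted in total cost but vanishes from the difference, which is the only quantity the ICER uses.

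The documents show that such costs exist. Section 6.2 has a point-of-care creatinine machine carried to Arm A meetings. Section 6 has the clinical officer reviewing records and preparing drugs before each visit, and section 6.2 has data transferred to the medical record afterwards. Addendum item 2 thinned the visit schedule "to reduce administrative burden on clinical officers and study staff traveling to remote community meeting locations".

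Staff time raises a related question. "Clinical care unit costs will be estimated by multiplying the time of the clinical interaction (based on time motion logs") by salaries and overhead. Travel, preparation and record transfer are not named in that unit cost, and overhead is not defined. These items could be in the overhead, in the tracking tool, in the pooled fixed costs, or nowhere.

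At stake is the provider-perspective cost difference, and with it the cost per suppressed patient, per retained patient and per DALY, the last of which is judged against income per capita.

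**Working it through.** The documents give no cost figure, so there is nothing to reproduce. The check is algebra on the allocation rule.

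**Inputs.** Planned arm sizes A = 450, B = 450, C = 300, total 1,200 (section 3.4.1). F is a fixed cost incurred only for Arm A. G is a fixed cost incurred only for facility care (Arms B and C, 750 participants). Both are unknown.

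**Step 1: an Arm A-only cost F under four readings**

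| Allocation | A vs B | A vs C | B vs C |
|---|---|---|---|
| To Arm A only | F/450 | F/450 | 0 |
| Per head over all 1,200 | F/1200 − F/1200 = 0 | 0 | 0 |
| Per head over the 900 in A and B | F/900 − F/900 = 0 | F/900 (half of F/450) | F/900 (should be 0) |
| By visits over all 1,200 | partial, see step 2 | partial | 0 if B and C have equal visits |

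The third row is there because section 9.1 labels both microfinance arms as intervention arms.

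**Step 2: sharing by visits.** With a visits per Arm A participant and v per control participant, the share of F/450 kept in A vs B is 450 × (a − v) / (450a + 750v). The section 2 schedule gives a = 11 (months 0 to 6, then 9, 12, 15, 18). The Addendum item 2 schedule for Busia Phases II to IV gives a = 9 (months 0, 1, 2, then 3 to 18 quarterly). The documents do not give v, so 4 to 9 is an assumed range.

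| v | a = 11 | a = 9 |
|---|---|---|
| 4 | 450×7/7,950 = 39.6% | 450×5/7,050 = 31.9% |
| 6 | 450×5/9,450 = 23.8% | 450×3/8,550 = 15.8% |
| 7 | 450×4/10,200 = 17.6% | 450×2/9,300 = 9.7% |
| 9 | 450×2/11,700 = 7.7% | 0% |

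**Step 3: direction when facility costs are pooled too.** Arm-specific allocation gives F/450 − G/750 for A vs B. Per-head pooling gives 0 whatever F and G are. With an assumed F = 45,000 USD:

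- G = 0: 100 − 0 = +100 per head
- G = 37,500: 100 − 50 = +50
- G = 75,000: 100 − 100 = 0
- G = 150,000: 100 − 200 = −100

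Pooling understates the increment in the first two cases, is harmless in the third, and overstates it in the fourth.

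**Step 4: size, for illustration only.** F from 20,000 to 60,000 USD is 20,000/450 = 44 to 60,000/450 = 133 USD per Arm A participant. With F = 45,000, G = 0, an assumed variable-cost difference of 20 USD and an assumed gain of 0.15 in suppression, the ICER is 20/0.15 = 133 pooled and (20 + 100)/0.15 = 800 arm-specific, per additional suppressed patient. A smaller gain widens the gap.

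**The case against.** The strongest reply is that the sentence is being read too literally. It does not say that the pool spans all three arms, and its base is undefined, so equal shares over 1,200 is an inference. Section 9.1 costs intervention and controls from separate sources, and section 10.2 treats programme equipment separately from unattributed organisational costs. On that view nobody would charge a project motorcycle to Arm C.

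Part of this stands: exact cancellation is the plain reading, but not the only one. It does not rescue the rule. Sections 9.1 and 10.2 describe data sources and costing steps; they do not assign a fixed cost to an arm, and so they pull against the section 9.2 sentence without replacing it. Section 8.1 counts all Aim 1 participants as the 900 microfinance members plus the 300 controls, which favours the wide reading. The narrower readings in steps 1 and 2 also fail to return the full F/450.

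A reader might go further and infer that the ICER is bound to be too favourable, or that every ICER is affected. The documents do not support either:

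- The pool names cleaning, maintenance, utilities and rent, so facility savings may cancel as well, and the net sign is open.
- For B vs C, an Arm A-only cost should contribute 0, and on the per-head reading over everyone it does.
- Section 7.1 measures blood pressure and HbA1c in both microfinance arms. Equipment shared by A and B properly cancels between them, and the text does not say which testing machines are meant.

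Nor can one say that travel is certainly lost, since it may be in the undefined overhead, or that equipment and travel are the main cost difference: no cost data are given.

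**Conclusion.** The concern holds in a limited form. As written, the rule can take fixed costs incurred only for Arm A out of the provider-perspective incremental cost: wholly for A vs B under either per-head reading, wholly or by half for A vs C, and by 60% or more for A vs B in the visit-based cases tried. As far as those costs go, the MF+ICB ICER is too favourable. The net direction is not established, because pooled facility costs make the omitted term F/450 − G/750.

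The cancellation is algebraic and does not depend on F. The figure F/450 rests on the planned arm sizes, and the dollar amounts are assumptions. The planned sensitivity analyses vary model parameters and do not name the allocation rule, so they would not clearly expose the problem. Patient costs and the government and donor estimate are described separately, and the Aim 1 comparison is untouched. Severity is moderate.

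**What to change.** Replace the allocation sentence in section 9.2 with: *Fixed costs are assigned to the arm or arms that incur them and divided among those arms' participants. Only costs shared by several arms are spread over the participants of those arms, on a stated base. Research-only costs are excluded.*

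In addition:

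- State that clinical-officer travel, visit preparation and record-transfer time are counted once, in the Arm A cost, and define what overhead contains.
- Reconcile sections 9.1, 9.2 and 10.2 so that one rule applies throughout.
- Add a sensitivity analysis on the rule, showing the ICER under arm-specific, per-head and visit-based allocation.

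The cost is tagging entries in the existing cost tracking tool by arm; no new participant data are needed. The Arm A incremental cost may become less favourable.

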The original analysis plan used a generalized linear model as the primary analysis method. The change in the analysis plan was made without looking at within arm data, but was made after the high rate of viral suppression was known (i.e., overall outcome prevalence was known but no between arm comparisons had been done). The reason for the change was: We have partially clustered data as the individuals in Arms MF+ICB and MF+UC are in clusters while participants in the UC arm are not. The mixed effects model requires correct specification of the distribution assumptions of random effects while the GEE does not. As verifying the distribution assumptions on people in a single cluster is impossible, we thought a GEE would provide a better approach. A recent manuscript compared methods for analyzing partially clustered data and concluded "Analysis of partially clustered trials using GEEs with an independence working correlation structure may be preferred to avoid the limitations of mixed models and exchangeable GEEs" further supporting the change (this was published after the decision was made to change the analysis method).

⁸ Prague M, Wang R, Stephens A, Tchetgen Tchetgen E, DeGruttola V. Accounting for interactions and complex inter-subject dependency in estimating treatment effect in cluster-randomized trials with missing outcomes. Biometrics. Published online 2016. doi:10.1111/biom.12519

⁹ Lange, K. M., Sullivan, T. R., Kasza, J., & Yelland, L. N. (2024). Performance of mixed effects models and generalized estimating equations for continuous outcomes in partially clustered trials including both independent and paired data. Statistics in Medicine.

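### The Aim 3 cost-effectiveness labels have no sign convention or dominance rule, so a costlier and less effective arm can receive the most favourable label

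*Combined protocol and SAP*

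**What the plan says.** Section 9.1 introduces the numerator: "The differences in costs among the control and intervention arms will be defined as the incremental costs". Section 9.2 introduces the effect, which "will be defined as the difference in outcomes between the SOC and the intervention groups". Neither sentence says which arm is subtracted from which. Section 9.2 then states: "Incremental Cost-Effectiveness Ratio (ICER) will be defined as incremental cost over incremental effectiveness". On the DALY scale, "we will model incremental costs per disability-adjusted life year (DALY) averted".

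The verdict rule follows: "We will compare the cost per DALY saved to the Kenyan income per capita (GDPpc) and deem the intervention extremely cost-effective if" the dollars per DALY figure "is less than 1*GDPpc, highly cost-effective if" it is below three times GDP per capita. Both cuts are upper limits.

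The same section says that the final results will be ratios of each intervention against standard care. It mentions a net-benefits estimation once, in the sentence on conversion to constant 2018 USD. It also plans one-way, multi-way, threshold and probabilistic sensitivity analyses. None of these says how a negative ratio, or a ratio of two negative increments, is to be read.

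**The concern.** A ratio loses the signs of its two parts. A negative value can mean cheaper and better or dearer and worse. A positive value can mean paying for a gain, or saving money by accepting a loss. An upper limit on the ratio gives the right answer only when both increments are positive.

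The setting makes the other quadrants worth planning for. Section 3.4.2 assumed suppression of 20 to 50% in the microfinance standard-care arm and a 15% increase. The Addendum (item 10, reasons for revising the analysis plan) says that the change of method "was made after the high rate of viral suppression was known". High overall suppression leaves little room for a gain, so an effect estimate near or below zero has to be allowed for. Section 9.2 also costs the intervention from the patient's side, including time and transport, where the incremental cost could be negative.

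At stake is the published Aim 3 label: a result that should count against the intervention could be reported under the strongest favourable term in the plan.

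**Working it through.** **Inputs.** The ratio and the two cuts come from section 9.2. The documents give no GDP per capita, incremental cost or DALY figure, so there is no stated result to reproduce. Assumed for illustration: GDP per capita of 1,000, 2,000 and 3,000 USD, and the increments in the table, all taken as intervention minus comparator.

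**Formulas.** Ratio = ΔC / DALYs averted. Label: *extremely* if the ratio is below 1 × GDPpc, otherwise *highly* if below 3 × GDPpc. Net monetary benefit: NMB = λ × DALYs averted − ΔC, where λ is the threshold.

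| Result | ΔC (USD) | DALYs averted | Ratio | Label at GDPpc 1,000 / 2,000 / 3,000 | NMB at λ = 1 × GDPpc |
|---|---|---|---|---|---|
| Dearer, better | +100 | +0.02 | 5,000 | none / highly / highly | −80 / −60 / −40 |
| Dearer, worse (dominated) | +100 | −0.02 | −5,000 | extremely in all three | −120 / −140 / −160 |
| Cheaper, better (dominant) | −100 | +0.02 | −5,000 | extremely in all three | +120 / +140 / +160 |
| Cheaper, worse, small saving | −10 | −0.2 | 50 | extremely in all three | −190 / −390 / −590 |
| Cheaper, worse, large saving | −1,000 | −0.02 | 50,000 | none in all three | +980 / +960 / +940 |

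**What does not depend on the assumed figures.**

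1. If ΔC > 0 and DALYs averted < 0, the ratio is negative and lies below any positive GDPpc. The label is always *extremely*, while NMB is negative for every λ > 0.
2. If both are negative, the ratio is the saving per DALY lost. Ratio < λ means |ΔC| < λ × |DALYs|, which is the condition for NMB = |ΔC| − λ × |DALYs| to be negative. At the first cut the rule is therefore reversed in this quadrant: it gives the top label to the results with negative net benefit at 1 × GDPpc.
3. If both are positive, ratio < λ and NMB > 0 are the same condition, and the rule works.

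**Dependence on the order of subtraction.** If ΔC is intervention minus comparator but the effect is comparator minus intervention, the dominated arm gives +100 / +0.02 = +5,000. The first row, dearer and better, then gives +100 / −0.02 = −5,000 and takes the top label. Mixing the orders moves the fault to another quadrant.

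**Effect on a probabilistic analysis.** One million draws were taken with assumed ΔC ~ N(100, 20) and DALYs averted ~ N(μ, 0.02), and the written rule was applied to each draw:

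| μ | Labelled *extremely*, GDPpc 1,000 / 2,000 / 3,000 | NMB > 0 at 1 × GDPpc |
|---|---|---|
| 0 | 50.0% / 51.2% / 55.7% | 0.0% / 1.3% / 5.7% |
| −0.02 | 84.1% / 84.2% / 84.8% | 0.0% / 0.1% / 0.6% |

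The gap between the columns is the share of dominated draws, about 50% and 84%. This describes how the rule behaves, not what this trial will show.

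**The case against.** The strongest reply is that the rule concerns cost per DALY saved or averted, which presupposes that DALYs are averted. If none are, there is no such cost to compare, and a competent health economist would report dominance. That is probably what would happen. But the wording names a quantity without setting a condition on its sign, and a prespecified verdict should not need to be overridden once the result is known.

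The second reply is that the plan goes beyond the ratio. This stands in part. It would be wrong to infer that net benefit appears only as a currency step: the conversion serves a net-benefits estimation that is itself planned. The threshold and probabilistic analyses would also give context, so a reader would not be left with a bare label. The remaining gap is that net benefit has no formula, none of these analyses has a dominance rule, and none is linked to the verdict.

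The third reply is that the negative ratio depends on a sign convention that sections 9.1 and 9.2 do not fix. That is correct, and it is part of the defect.

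**Conclusion.** The point holds for the rule as written, on one assumption: both increments are taken as intervention minus comparator. A dominated arm then always receives the most favourable label, indistinguishable from a dominant one, and the cheaper, less effective quadrant is misread as well. The size of the problem is the wrong verdict in two of the four quadrants; no assumed figure is needed for that.

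A reader might go further and infer that a mislabel is likely, or attach a probability to it. The documents do not support that. With 382.5 participants per arm (450 less 15% dropout), a design effect of 1.95 and a true gain of 2 points, the chance of a negative estimate of the suppression difference between the two microfinance arms is 28%, 24% or 16% at assumed suppression of 85%, 90% or 95%. With no true effect it is 50%. These figures show only that a negative suppression estimate is possible. They use the planned 40 groups, whereas the Addendum reports 57 randomised. They compare the two microfinance arms, whereas the final ratios are against standard care. They concern suppression, whereas the verdict uses DALYs modelled over the life span, with retention also an effectiveness outcome. A dominated result also requires a positive incremental cost.

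The scope is Aim 3. The primary viral suppression analysis is unaffected.

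**What to change.** In section 9.2:

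1. Define incremental cost and DALYs averted both as intervention minus comparator, so that a positive DALY figure is a health gain, and name the comparator for each contrast.
2. Report the quadrant of each result, naming dominant and dominated results as such.
3. Base the verdict on incremental net monetary benefit (threshold × DALYs averted − incremental cost) at 1 and 3 times GDP per capita. Give this as the formula for the net-benefits estimation already planned.
4. Summarise the planned probabilistic analysis as the probability that net monetary benefit is positive at each threshold.
5. Keep reporting ratios as planned, but apply the two labels to the ratio only when incremental cost and DALYs averted are both positive.

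In the dominated example this gives −120, −140 and −160 USD at 1 × GDPpc and −160, −220 and −280 USD at 3 × GDPpc (GDPpc assumed at 1,000, 2,000 and 3,000 USD), so the favourable label disappears. The cost is a few sentences, with the same inputs and no new data.
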